### 3.2.2 Objective 2 Outcome Measures

Outcome measures to be used are listed in the table below. Of the 80 patients participating in the study, we believe that 90% will complete the outcome measures at baseline and all follow-up periods and report the burden of completing these is acceptable.

Outcome Domain	Measure
Primary	
Pain severity	Graded Chronic Pain Scale (GCPS) with mean intensity ratings for reported current, worst, and average pain. 
Jaw Functioning	Jaw Functional Limitation Scale (JFLS-8) identifies daily activities interfered with by jaw pain. 
Secondary	
Pain interference	Graded Chronic Pain Scale
Pain timing	Symptom Severity Index

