Intervention (adherence/compliance)	
 
1. Number of participants accessing all online lessons
 
2. Use of health coaches (PACT arm)
 
3. Pain and risk assessment instruments within the PACT program (PACT arm)
 
4. Time spent in online program per week (PACT arm)
 
	
 
1. 80% of enrolled participants access all lessons as measured by Web site hits
 
2. 90% of participants in PACT have at least 3 phone meetings with the health coach (PACT arm)
 
3. Completion of all pain and risk assessment instruments within the PACT program (PACT arm)
 
4. Time spent in each module of online program per week (PACT arm)
 

- c. Completion of questionnaires at 8-week and 16-week follow-ups, and program evaluation. Completion of questionnaires will be measured by the percent of participants who complete the 8-week and 16-week follow-up questionnaires and, the program evaluation. We expect that at least 80% of participants will complete all questionnaires.

Objective	Constructs	Target outcomes
Evaluation (adherence/compliance)	
 
1. Number of participants completing 8-week and 16-week follow-up questionnaires
 
2. Number of participants completing the program evaluation survey questions (PACT arm)
 
	
 
1. 80% complete both 8- and 16-week follow-up questionnaires
 
2. 80% of participants in PACT group complete the program evaluation form
 

Evaluation (instrument performance)	
 
1. Responsiveness to constructs in subscales of the survey.
 
2. Inter-correlations between scales
 
3. Participant burden is measured by time to complete.
 
	
 
1. Outcome variables show changes in the expected direction
 
2. Outcome variables are associated with mediator/moderator factors in the expected direction
 
3. 90% of participants complete all surveys in estimated time
 

- d. Participant perceptions of the online website functionality and acceptability will be measured by participant reports of problems and ease of use reported at the program

evaluation. These reports will come from the number of phone calls/questions received about web-site issues, and from the qualitative interview.

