### 3.2.3 Objective 3 Outcome Measures

#### 3.2.3.1 Hypothesized mediators

Of the 80 patients participating in the study, we believe that 90% will complete the mediator questionnaire at baseline and all follow-up periods and report the burden of completing these is acceptable. Specific measures of self-efficacy, participant activation, exercise frequency, and sleep quality will be made by questionnaires, as described in section 8.1.1.

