#### 3.2.3.2 Hypothesized moderators

Of the 80 patients participating in the study, we believe that 90% will complete the moderator measures at baseline and all follow-up periods and report the burden of completing these is acceptable. Specific measures of disability status, catastrophizing, depression, oral habits, perceived stress, and social support will be made by questionnaires, as described in section 8.1.1.

Outcome Measures including Data Constructs, Scales, Sources and intervals.								
	Construct	Scale/ Variable	Data Source	Target	Baseline	Intervention	Weeks from baseline	Weeks from baseline
Timing (weeks)					At Enrollment	0-8 wks.	8 wks.	16 wks.
Screening	Eligibility	DC-TMD Pain Screener and self-report criteria	Phone Screen	Potential participants screened	X			
	Demo-graphics	Age, marital status, education, employment,	Phone screen	Potential participants screened	X			

Outcome Measures including Data Constructs, Scales, Sources and intervals.								
	Construct	Scale/ Variable	Data Source	Target	Baseline	Intervention	Weeks from baseline	Weeks from baseline
Timing (weeks)					At Enrollment	0-8 wks.	8 wks.	16 wks.
Other Descriptive Information	Prior Medical Conditions	Prior Medical Conditions	On-line survey	Participants	X			
Objective 1 Process Evaluation	Recruitment	Contact/consent	Survey Center logs	Participants	X			
	Compliance/adherence	Self-report of intervention practice	On-line Survey	Participants		X		
	Compliance/adherence	Program evaluation form	On-line survey	Participants			X	
	Acceptability	Heuristic evaluation of ease of use and functionality	Web hits Survey	Participants			X	
	Participant experience	Barriers and facilitators to adherence	Qualitative interview	Participants		X	X	X
Objective 2 Primary Outcomes	Pain Severity	Graded Chronic Pain Scale-severity (7 items; of 10)	On-line survey	Participants	X	X	X	X
	Jaw Function	Jaw Functional Limitation Scale (JFLS-8; items; short version)	On-line survey	Participants	X	X	X	X
Objective 2 Secondary Pain Outcomes	Pain interference	Graded Chronic Pain Scale-intensity (3 items of 10)	On-line survey	Participants	X	X	X	X
Objective 3 Mediators	Self-efficacy	Chronic Pain Self-efficacy Questionnaire (5 item Self-efficacy for Pain management (PSE) scale)	On-line survey	Participants	X	X	X	X

Outcome Measures including Data Constructs, Scales, Sources and intervals.								

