## 8-week follow-up Survey including Program Evaluation Questions (PACT ONLY)

**Thank you for participating in the TMD Self-Care Study. The following questions are about your experiences with this study and should take about 5-10 minutes to answer. The first questions are about your jaw and temple pain. Please answer all the questions as best as you can.**

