Tailored Self-Management of TMD Pain using Health Information Technology

NIDCR Protocol Number: 16-054-E

NIDCR Grant Number: U01 DE025609

Principal Investigator: [name], MS

March 20, 2017

Final Analysis Plan

We will perform the following analysis and present results in preparation of the full study. The Primary outcomes for this study are acceptability and feasibility of the methods. The study is not sufficiently powered to test for mean changes from baseline to follow-up. Thus, we will conduct the following descriptive analysis at noted in the outcome measures:

- Number of participants, baseline characteristics and outcomes at baseline will be summarized descriptively
- Summary measures will include mean values (standard deviation SD) for continuous variables and frequency distribution for categorical variables.
- Outcome measures will be analyzed for departure of normality, and standard transformations will be applied.
- Percent of participants completing the measures for outcomes, mediating and moderating factors at baseline and each follow-up periods

The acceptability of the outcomes, mediating and moderating measures at baseline and followup periods

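### Participants are expected to report that the questionnaire burden is acceptable, but no printed survey or interview item asks them, and the time target that measures burden has no defined estimate

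*Protocol*

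**What the plan says.** Section 3.2.2 gives the investigators' expectation for the 80 participants: "90% will complete the outcome measures at baseline and all follow-up periods and report the burden of completing these is acceptable". Section 3.2.3.1 repeats it for mediators ("90% will complete the mediator questionnaire at baseline and all follow-up periods and report the burden of completing these is acceptable") and section 3.2.3.2 for moderators ("90% will complete the moderator measures at baseline and all follow-up periods and report the burden of completing these is acceptable").

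The SAP, and Protocol section 11.4 in matching terms, list two separate outputs. One is the percentage completing each set of measures. The other is "The acceptability of the outcomes, mediating and moderating measures at baseline and followup periods". No item, scale, threshold or denominator is given for the second.

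The one operational definition of burden is in section 3.2.1(c), in the row on instrument performance: "Participant burden is measured by time to complete". The matching target is that "90% of participants complete all surveys in estimated time". The estimated time is not stated there. Each of the four survey forms printed in Appendix G opens with the same sentence: "The following questions are about your experiences with this study and should take about 5-10 minutes to answer".

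**The concern.** Sections 3.2.2 and 3.2.3 call for something participants say about the questionnaires. The SAP keeps acceptability apart from completion, so completion was evidently not meant to stand in for it. If no instrument asks the question, that output has no self-report behind it. The pilot would then have to infer acceptability from who finished and how long they took.

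This matters because feasibility and acceptability are the primary outcomes, and Objective 2 is about whether these measures can be used in the multisite trial. Views on burden cannot be recovered reliably once data collection has ended.

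**Working it through.** **Step 1. What each printed instrument asks.**

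| Instrument | Who | Subject |
|---|---|---|
| Item 22a–g (8-week forms; also printed on the form headed as baseline) | Both arms | Program information, its value, ease of navigation |
| Item 23a–k (8-week) | PACT only | Modules, in-program self-assessments, time demanded by the program |
| Items 24–25 (8-week) | PACT only | Helpfulness of program components |
| Items 26–27 (8-week) | PACT only | Open text on the program |
| Item 28 (8-week) | PACT only | Invitation to an interview |
| 16-week form | Both arms | No evaluation items; ends after the exercise questions |
| Appendix H guide | PACT interviewees (section 7.1.2.2 plans ten or more) | Program, coach, modules; question 17 asks whether end-of-module assessments helped |
| Reminder calls, section 6.4 | Late completers only | Barriers to completion; no form |

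The nearest items are 23h (time commitment to the program) and interview question 17. Neither concerns the outcome, mediator or moderator questionnaires, and both are limited to PACT. Open comments could raise burden spontaneously, but they are also PACT-only and give no denominator for a 90% figure.

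**Step 2. The size of the expectation.** 0.90 × 80 = 72 participants. If a burden item existed and exactly 72 of 80 endorsed it, the 95% Wilson interval would be 81.5% to 94.8%. As printed, there is no count to put in the numerator.

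**Step 3. The time measure.** The documents give no inputs from which 5 to 10 minutes could be derived, so that figure cannot be reproduced. The printed items can be counted, one per response field:

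- 16-week form: 8 (graded pain) + 8 (jaw function) + 5 (self-efficacy) + 7 (activation) + 2 (sleep) + 4 (exercise) = 34.
- 8-week form: 34 + 7 (item 22) = 41. The form headed as baseline also has 41 as printed.
- 8-week PACT-only form: 41 + 11 (item 23) + 7 (item 24) + 3 (item 25) + 2 (items 26–27) + 1 (item 28) = 65.

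Seconds available per item at the 10-minute limit are 600 / n: 17.6 for 34 items, 14.6 for 41 and 9.2 for 65. The longest form has 65 / 34 = 1.91 times the items of the shortest under the same printed estimate. One 10-minute limit therefore means a different thing on each form, and the target does not say which form or block it applies to.

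**Step 4. Why the denominator matters once an item exists.** Only people who reach the end of a survey will answer an item placed there. As an illustration, take section 3.2.1(c)'s follow-up completion target of 80%: 0.80 × 80 = 64. If all 64 agreed, the result would be 64/64 = 100% of completers but 64/80 = 80% of those randomised.

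**The case against.** **The protocol already defines burden as time to complete.** This is correct: time is the protocol's own measure under Objective 1, not a substitute for something else. The SAP line does not itself require self-report either, and could be filled from completion, timing and reminder calls. But sections 3.2.2 and 3.2.3 say that participants "report the burden of completing these is acceptable", and elapsed time is not a report.

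**The 90% is an expectation.** It is worded as what the investigators believe, and no go/no-go decision hangs on it. Objectives 2 and 3 themselves speak of capturing measures accurately. A reader might infer that half of a success criterion is lost; the documents do not set up such a criterion.

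**The printed forms may not be the fielded ones.** This has force. The form headed as baseline carries program-evaluation items and promises a $35 card, where Appendix E gives $20 for the initial survey. It also prints none of the moderator scales scheduled at baseline. Section 7.1.2.2 describes 9 interview questions and Appendix H prints 18. Module comment sections and weekly assessments are not printed. A reader might infer that none of the 80 will be asked at any visit; that cannot be shown. The finding is limited to the instruments as printed.

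**The estimate may be elsewhere.** Linking the target to 5 to 10 minutes is an inference. The consent pages and the Manual of Operations are not in the available text and could give another figure.

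**The arms may not be treated unequally.** A reader might infer from 41 against 65 items that PACT is set up to miss the time target. The documents do not support this. The outcome and mediator block is 34 items in both arms, the program evaluation has its own completion target, the time target is pooled, and no arm comparison of it is planned. Section 7.1.2.1's 7 + 11 evaluation questions would give 34 + 18 = 52 items, not 65. At equal pace per item, anyone who would finish 41 items within 10 × 41 / 65 = 6.3 minutes would also finish 65 within 10.

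**Survey timing may be recorded.** Section 12's list of tracked web activity names page access but not survey duration. The list is not exhaustive, and section 3.2.1(b) plans time per module. Survey timing is unstated, not shown to be unavailable.

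**Conclusion.** The point holds as a mismatch between a stated participant report and the printed instruments. Three sections expect 90% of 80 (72 people) to report acceptable burden, and the SAP lists acceptability apart from completion. No printed survey or interview question would produce that report in either arm. The gap is clearest at 16 weeks, where the form has no evaluation items although the expectation covers every follow-up.

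The secondary point is that the time target needs a defined estimate. The only one in the available text is the same 5 to 10 minutes for 34, 41 and 65 printed items. This does not establish that the target is unreachable, or that it is biased between arms.

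The conclusion assumes that the instruments in use match those printed in Appendices G and H. It should be acted on, because the missing information cannot be collected reliably afterwards; it does not undermine the other planned descriptive analyses.

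**What to change.** 1. Add one closed item on questionnaire burden to the end of the baseline, 8-week and 16-week surveys in both arms, using item 22's agree/disagree scale. For example: *the effort of filling in these questionnaires was acceptable to me*. The baseline item is the one that can cover the moderator scales, since the outcome-measures table in section 3.2.3.2 schedules them at baseline only.
2. Define acceptable as Agree or Strongly agree. Report the percentage over all 80 randomised participants as well as over completers, because non-completers will not answer it.
3. Name this item as the source for the expectation in sections 3.2.2, 3.2.3.1 and 3.2.3.2 and for the acceptability line in the SAP and section 11.4.
4. State that the website records survey start and submit times. Apply the time target to the outcome/mediator block common to all forms, or state an estimate for each form.

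The cost is one item per survey, a pair of timestamps, a short SAP edit, and a few seconds of participant time per survey.

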### 3.2.3 Objective 3 Outcome Measures

#### 3.2.3.1 Hypothesized mediators

Of the 80 patients participating in the study, we believe that 90% will complete the mediator questionnaire at baseline and all follow-up periods and report the burden of completing these is acceptable. Specific measures of self-efficacy, participant activation, exercise frequency, and sleep quality will be made by questionnaires, as described in section 8.1.1.

#### 3.2.3.2 Hypothesized moderators

Of the 80 patients participating in the study, we believe that 90% will complete the moderator measures at baseline and all follow-up periods and report the burden of completing these is acceptable. Specific measures of disability status, catastrophizing, depression, oral habits, perceived stress, and social support will be made by questionnaires, as described in section 8.1.1.

Outcome Measures including Data Constructs, Scales, Sources and intervals.								
	Construct	Scale/ Variable	Data Source	Target	Baseline	Intervention	Weeks from baseline	Weeks from baseline
Timing (weeks)					At Enrollment	0-8 wks.	8 wks.	16 wks.
Screening	Eligibility	DC-TMD Pain Screener and self-report criteria	Phone Screen	Potential participants screened	X			
	Demo-graphics	Age, marital status, education, employment,	Phone screen	Potential participants screened	X			

Outcome Measures including Data Constructs, Scales, Sources and intervals.								
	Construct	Scale/ Variable	Data Source	Target	Baseline	Intervention	Weeks from baseline	Weeks from baseline
Timing (weeks)					At Enrollment	0-8 wks.	8 wks.	16 wks.
Other Descriptive Information	Prior Medical Conditions	Prior Medical Conditions	On-line survey	Participants	X			
Objective 1 Process Evaluation	Recruitment	Contact/consent	Survey Center logs	Participants	X			
	Compliance/adherence	Self-report of intervention practice	On-line Survey	Participants		X		
	Compliance/adherence	Program evaluation form	On-line survey	Participants			X	
	Acceptability	Heuristic evaluation of ease of use and functionality	Web hits Survey	Participants			X	
	Participant experience	Barriers and facilitators to adherence	Qualitative interview	Participants		X	X	X
Objective 2 Primary Outcomes	Pain Severity	Graded Chronic Pain Scale-severity (7 items; of 10)	On-line survey	Participants	X	X	X	X
	Jaw Function	Jaw Functional Limitation Scale (JFLS-8; items; short version)	On-line survey	Participants	X	X	X	X
Objective 2 Secondary Pain Outcomes	Pain interference	Graded Chronic Pain Scale-intensity (3 items of 10)	On-line survey	Participants	X	X	X	X
Objective 3 Mediators	Self-efficacy	Chronic Pain Self-efficacy Questionnaire (5 item Self-efficacy for Pain management (PSE) scale)	On-line survey	Participants	X	X	X	X

Outcome Measures including Data Constructs, Scales, Sources and intervals.								
	Construct	Scale/ Variable	Data Source	Target	Baseline	Intervention	Weeks from baseline	Weeks from baseline
Timing (weeks)					At Enrollment	0-8 wks.	8 wks.	16 wks.
	Participant Activation	Patient Activation Measure (PAM; 7-items)	On-line survey	Participants	X	X	X	X
	Exercise	Global Physical Activity Questionnaire (2 questions)	On-line survey	Participants	X	X	X	X
	Sleep quality	WHO World Health Survey (4 questions)	On-line survey	Participants	X	X	X	X
Objective 3: Moderators	Catastrophizing	Pain Catastrophizing Scale (PCS; 14 items)	On-line survey	Participants	X			
	Depression	Patient Health Questionnaire (PHQ8; 8 items)	On-line survey	Participants	X			
	Oral habits	DC/TMD Oral Behavioral Checklist (15 items)	On-line survey	Participants	X			
	Stress	Perceived Stress Scale (PSS; 10 items)	On-line survey	Participants	X			
	Social Support	Social Support Questionnaire (SSQ; 6 items)	On-line survey	Participants	X			

#### **4 STUDY DESIGN**

The pilot study design is a 2-arm randomized clinical trial to test the methods that will be used in a future proposal for a full-scale multi-site clinical trial.

Eighty participants with TMD will be recruited through 2 recruitment protocols (1-Inbound recruitment or self-referral and 2-outbound recruitment or ICD-9/ICD-10 code identification) and randomized in a 1:1 ratio to the PACT program or Traditional self-care. Participants will be aged 18 or older because significant adjustments would need to be made to the program to take into consideration the differing cognitive status and developmental age, and limited to English-speakers because one of the primary outcome instruments is only validated in English.

The study should be completed in 12-18 months, with enrollment occurring for 8 months.

Participants will be evaluated for eligibility over the telephone following verbal consent for screening, and information including demographics and eligibility criteria. Eligible participants will be consented over the telephone and will sign the consent electronically. Following consent participants will complete the baseline questionnaire and be randomized to PACT (intervention) or self-care (control). Weeks 1-8 (intermediate visits) will consist of weekly website visits. Participants in the self-care arm will be provided with traditional self-care material. Participants in the PACT arm will complete initial assessments for weekly lessons, and based on the assessment will be provided personalized lessons. Participants in the PACT arm will also receive weekly coaching sessions by phone. All participants will participate in usual care from their dentist and will be asked to limit concomitant medications to NSAIDs. Participants in both arms will complete follow-up measures at 8 and 16 weeks post-intervention. Following the 8-week follow-up participants will be asked to complete a program evaluation, and at least 10 randomly-selected subjects will complete a qualitative interview.

Data analysis will evaluate feasibility and acceptability of the primary intervention and determine the utility of the outcomes measures that will be collected at baseline, 8-week and 16-week follow-ups.

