Objective	Constructs	Target outcomes for both arms
Web-Site functionality	
 
1. Heuristic evaluation of functionality of the Web-based platform
 
2. Mode of administration acceptance
 
	
 
1. Less than 10% of participants note problems with website via comments section in each module or during program evaluation
 
2. 90% of participants rate web-site accessibility for learning the concepts as very good to excellent
 

Intervention (acceptability)	
 
1. Identification of self-reported barriers for improvement
 
2. Pace in which participants complete the program
 
	
 
1. 80% of participants identify at least one self-report barrier for improvement
 
2. 60% of participants follow the timeline on the Web site to complete in 8 weeks
 

Participant perceptions of program	
 
1. Qualitative interviews of participants
 
	
 
1. At least ten randomly selected participants will agree to be interviewed to provide their perceptions about the content of the program and at least 90% report that it is acceptable.
 

- e. Participant perception of health coaches in the PACT program will be evaluated by qualitative interviews of both health coaches and participants

Objective	Constructs	Target outcomes for both arms
Participant perceptions of health coach	
 
1. Qualitative interviews of participants about health coaches
 
	
 
1. At least ten randomly selected participants will agree to be interviewed to provide their perceptions about the content of the program. Of at least 10 participants interviewed, 90% will report that they found the health coaches to be helpful.
 

---

Health coach perception of program	1. Qualitative interviews of participants	1. Health coaches will provide their perceptions on the program and areas for development
------------------------------------	---	---

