### **B. PACT Experimental Arm**

1. Participants randomized to the PACT care arm will be electronically directed to the PACT website landing page which explains each step of the process. Participants will complete the initial PACT assessment for each lesson. Based on the assessment, the PACT website will provide personalized training lessons for each participant.
2. Participants will also participate in weekly phone coach sessions.
3. Participants will complete each lesson on a weekly basis in order to focus on, understand, and implement the steps in each lesson. New material will only be made available to participants every 7 days.
  - a. If participants fail to complete a lesson, they will be prohibited from accessing all future materials until the missed lesson is completed, even if it takes more than one week.
  - b. Participants who fail to complete each lesson within a month will be called by the study coordinator to identify if problem exists and may result in study withdrawal.
4. Participant will also continue participate in usual care from their dentist such as a splint or anti-inflammatory medications as needed. Some patients may be under care of another healthcare provider such as a physical therapist.
5. Adverse events will be recorded through the website assessments.

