## **6.4 Final Study Visits (Final Visits, Weeks 8 and 16)**

All participants will be asked to complete the final follow-up outcomes evaluation at 8 weeks from the beginning of the intervention and at 16-weeks (2 months after program end). This includes questions about any adverse events and outcomes as reported by the participants during or after the lessons.

Participants will receive weekly email reminders from the web-system to complete the post-intervention questionnaires. There is a 2-week window in the completion of questionnaires at the 8-week and 16-week post-intervention time periods. If the questionnaire has not been completed at the 2-week period, participants will receive up to 3 reminder calls from the study coordinator to identify the barrier to completing the questionnaires and facilitate its completion.

If after two more weeks of time have passed without completion, the questionnaire will be not evaluable, and therefore, considered missing data.

At the end of the 8 week outcome questionnaire, participants will complete several program evaluation questions. In addition, at least ten randomly-selected subjects will complete a semi-structured qualitative interview about their experience in the program.

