## **12 SOURCE DOCUMENTS AND ACCESS TO SOURCE DATA/DOCUMENTS**

There are five main data instruments:

1. TMD phone Screening Form
2. Baseline questionnaire
3. 8-week Post-intervention questionnaire with program evaluation questions
4. 16-week Post-intervention questionnaire
5. Semi-Structured Interview (subgroup)

Data collection will occur at multiple points across the study period, including eligibility screening, the baseline questionnaire prior to the start of the intervention, 1st post-intervention questionnaire (week 8), and 2nd post-interventional questionnaire (week 16). Data will be collected electronically in both arms.

Web-based activity will be tracked in several ways using hits on the web-site pages including:

1. accessing each module within the web-site
2. accessing each self-report risk assessments
3. each weekly pain and function assessments
4. accessing the interactive components of the website including benefit balloons and barrier bricks

Audio-recorded, transcribed, and coded coaching sessions will be used to assess fidelity to the PACT intervention.

Study staff will maintain appropriate medical and research records for this study, in compliance with ICH E6, Section 4.9 and regulatory and institutional requirements for the protection of confidentiality of participants. Study staff will permit authorized representatives of NIDCR and regulatory agencies to examine (and when required by applicable law, to copy) research records for the purposes of quality assurance reviews, audits, and evaluation of the study safety, progress and data validity.

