to address any issues. Application can be monitored via alerting and monitoring tools that send notification to the system administrator whenever the application becomes inaccessible. Application uses open source version control system like SVN for source code version maintenance.

Application development uses the following tools/technologies/languages: Java, J2EE, JSP, Spring MVC Framework, Spring Security Framework, J2EE design patterns, jQuery, AJAX, Bootstrap framework, JavaScript, Oracle SQL/PLSQL, Log4j, jFree chart, JUnit, Apache Tomcat V7.0, Shell script, SVN, REDCap.

*Control Flow:* User log-in to the system using their unique user-id and password. For study participants after login, system presents a brief intro of study along with consent form. User gives his/her consent which is stored in the system data base; system then navigates to initial baseline survey form. Upon successful completion of the survey the survey results are stored in the database and based on pre-identified criteria system randomly assigns user to Usual-self-care arm or PACT arm; system takes user to their respective arm's program page. In the program page user has the opportunity to learn through the study modules. Based on user arm type, study modules present self-management lessons in the form of videos or slides. Once user completes the modules, then system prompts user to complete periodic (2month, 4month) surveys. The survey responses are stored in database and analyzed later to understand how the program has helped participants in improving TMD pain. Users of the application can use the contact information provided in the consent form to contact study coordinator in case of any navigation issues or application accessibility issues. Users can get new password/reset one using "forgot password" links.

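### The follow-up surveys have conflicting triggers: weeks 8 and 16 from the start in Section 6.4, but completion of the modules in the Appendix B website flow

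*Protocol*

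**What the plan says.** The reference point for the two follow-up surveys changes from place to place in the protocol.

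- **From the start.** Section 6.4 asks for them "at 8 weeks from the beginning of the intervention and at 16-weeks (2 months after program end"). The outcome table in Section 3.2.3.2 heads its 8- and 16-week columns "Weeks from baseline", and the Protocol Summary gives four months of participation.
- **From the end.** Section 4: "Participants in both arms will complete follow-up measures at 8 and 16 weeks post-intervention".
- **From completion.** The website control flow in Appendix B: "Once user completes the modules, then system prompts user to complete periodic (2month, 4month) surveys".

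Section 6.3 B sets the pace in the PACT arm. New material opens no more often than every 7 days, and for participants who leave a lesson unfinished, "they will be prohibited from accessing all future materials until the missed lesson is completed". No final deadline is given. A lesson unfinished after a month leads to a coordinator call and possibly withdrawal. Section 6.3 A describes no timed release or lock for the self-care material.

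Section 6.4 also sets the window: "There is a 2-week window in the completion of questionnaires at the 8-week and 16-week post-intervention time periods". It provides weekly email reminders and, once the window has passed, up to three calls. A survey still outstanding two weeks later counts as missing. None of these steps mentions module completion. The SAP has no rule on survey timing.

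**The concern.** A programmer working from Appendix B and a coordinator working from Section 6.4 would run different schedules. They agree only for a participant who keeps to one lesson a week.

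Three things are at stake:

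- Survey completion is an Objective 1 feasibility outcome (Section 3.2.1 c). If the site's prompt waits for the modules, low completion could reflect the trigger and be read as poor acceptability of the surveys.
- The pain and jaw-function items in Appendix G ask about the last 30 days. A survey that moves in time measures a different period.
- Section 11.2 wants the pilot to supply parameters for the multisite trial. Completion rates and scores would carry over less well if their timing followed adherence, and did so differently in the two arms.

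**Working it through.** **1. Which anchor reproduces the stated duration?** Take 1 month as 30.44 days (assumption).

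- From the start: 16 × 7 / 30.44 = 3.7 months, which rounds to the four months in the Protocol Summary. Eight weeks plus two months is 56 + 60.9 = 116.9 days, or 16.7 weeks, in line with the parenthesis in Section 6.4.
- Section 4 read literally, with an 8-week programme: 8 + 8 = 16 and 8 + 16 = 24 weeks. The last survey then falls at 24 × 7 / 30.44 = 5.5 months, which does not fit.

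**2. Where does the website rule part from Section 6.4?** If a PACT user averages p days per lesson, the eight lessons are done at week 8p / 7.

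| Days per lesson (p) | Modules done, week | Weeks past week 8 |
|---|---|---|
| 7 | 8.0 | 0 |
| 8.75 | 10.0 | 2.0 |
| 10.5 | 12.0 | 4.0 |
| 14 | 16.0 | 8.0 |
| 30 | 34.3 | 26.3 |

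Counted from week 8, the first survey stops being evaluable at 8 + 2 + 2 = 12 weeks, or 84 days. The limiting pace is 84 / 8 = 10.5 days per lesson. For the second survey the cut-off is 16 + 4 = 20 weeks, or 140 days. If its prompt comes at the later of week 16 and completion, the limiting pace is 140 / 8 = 17.5 days.

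If the window ran from the prompt instead, the survey would be late rather than missing: at 14 days per lesson, week 16 in place of week 8.

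**3. What do the plan's own targets allow?** Section 3.2.1 (d) aims for "60% of participants follow the timeline on the Web site to complete in 8 weeks", and Section 3.2.1 (b) for 80% accessing all lessons. Section 11.2 gives 40 per arm. If both targets were just met in the PACT arm:

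- past week 8 or never finished: 40 × (1 − 0.60) = 16
- never finished: 40 × (1 − 0.80) = 8, contained in the 16
- without a completion-triggered prompt by week 12: between 8 (every late finisher done by week 12) and 16 (none done by then). The documents give no distribution of pace to narrow this.

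**4. What would this do to the completion targets?** If only finishers were surveyed and 80% finished, the ceiling on completion would be:

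- PACT alone affected: (40 + 32) / 80 = 90%
- both arms affected: (32 + 32) / 80 = 80%

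The targets are 80% completing both follow-ups (Section 3.2.1 c) and 90% completing the outcome measures at every time point (Section 3.2.2). The first case leaves no room under the 90% target. The second leaves none under the 80% target and puts 90% out of reach.

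**The case against.** **Post-intervention is a label.** Section 12 lists a "1st post-intervention questionnaire (week 8), and 2nd post-interventional questionnaire (week 16"), Appendix A uses the same week numbers, and the telephone script in Appendix E tells participants two and four months. A reader might infer from Section 4 that the surveys are really planned for weeks 16 and 24. Nothing else in the protocol fits that. The objection stands, and the Section 4 conflict is mainly one of wording.

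**Section 6.4 reaches everyone.** Its request goes to all participants, and its emails and calls carry no module condition. Under Section 5.9 the coordinator also monitors follow-up questionnaires in both arms. The Appendix B sentence is descriptive and itself names the surveys by calendar month. A reader might infer that slow PACT users will be prompted late or never. The documents do not establish that. But they also do not say which rule prevails, or whether the survey page stays closed until the modules are done. If it does, a reminder cannot help.

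**The control arm may be gated too.** The usual-care screen in Appendix B lists eight steps and then the survey. So a completion trigger cannot be called a PACT-only feature. The difference that remains is pace: timed release and the sequential lock are described for PACT only.

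**The counts are complements of minimum targets.** The 60% target is headed as applying to both arms and the 80% target refers to all enrolled participants. Finishing after week 8 does not in itself lose a survey. All this stands, so 16 and 8 of 40 cannot be read as expected losses.

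**The analysis is descriptive.** Section 11.4 and the SAP state that the study is not powered for mean change. Completion is a percentage of participants, so unprompted non-finishers would lower the rate openly. A reader might infer that completion would be reported among adherent users only, and Section 3.2.1 (c) does not support that. What remains is the feasibility rate itself and the comparability of survey timing.

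**Conclusion.** The protocol holds two operational rules for the same surveys, a calendar date and completion of the modules, and does not rank them. They coincide at 7 days per lesson and diverge for anyone slower.

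The consequences are conditional on the website rule governing. The site's first prompt then comes after the week-12 cut-off for a PACT user averaging more than 10.5 days per lesson, and a non-finisher in either arm has no completion-triggered prompt. The 10.5-day figure also assumes that the 2 + 2 weeks run from week 8 after the start. How many people this touches cannot be derived from the documents, and the Section 6.4 reminders may recover some or all of them.

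This does not show that surveys will be lost or that a treatment comparison will be biased. It is worth correcting because a stated Objective 1 outcome could otherwise depend on adherence and arm through the survey trigger, and the correction is simple.

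**What to change.** Use one anchor in Sections 4 and 6.4 and in Appendices A and B: both surveys open on day 56 and day 112 from randomisation or baseline (name one), in both arms. This agrees with Section 6.4 and the outcome table.

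Add that survey prompts and access open by date, whether or not the modules are completed, and that the 2 + 2 week window runs from those dates. Define post-intervention as a label for these surveys, or drop it.

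The cost is wording in four places and a check of how the website is programmed, which the documents do not settle. If the surveys are gated by completion, a date trigger has to replace the gate. No extra data or participants are needed.
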